## LIST OF ABBREVIATIONS

BC-FMT	Bone Conduction – Floating Mass Transducer	
BCI	Bone Conduction Implant	
CFR	Code of Federal Regulations	
CNC	Consonant-Nucleus-Consonant	
CRF	Case Report Form	
FDA	Food and Drug Administration	
GCP	Good Clinical Practice	
HDSS	Hearing Device Satisfaction Scale	
HL	Hearing Level	
IC	Informed Consent	
IRB	Investigational Review Board	
PI	Principal Investigator	
PTA	Pure-Tone Average	
SAP	Statistical Analysis Plan	
SIN	Speech In Noise	
SNR	Signal-to-Noise Ratio	
SOP	Standard Operating Procedure	
SPL	Sound Pressure Level	
SSQ	Speech, Spatial and Qualities of Hearing	

## STATEMENT OF COMPLIANCE

The trial will be carried out in accordance with Good Clinical Practice (GCP), as required by the following:

- United States Code of Federal Regulations (CFR) applicable to clinical studies (21 CFR Part 50, 21 CFR Part 54, 21 CFR Part 56)
- Good Clinical Practices

All investigators involved in the conduct of this study will be informed about their obligations in meeting the above commitments.

PROTOCOL SUMMAR	Υ
Title:	Outcomes in Adults with Mixed or Conductive Hearing Loss Implanted
	with the BONEBRIDGE
Study Description:	Approximately thirty subjects with mixed or conductive hearing loss,
	meeting FDA-cleared candidacy criteria for the BONEBRIDGE, will be
	implanted and followed for three (3) months post-activation to assess
	safety and effectiveness of the BONEBRIDGE implant.
Objectives:	Primary: To assess safety and effectiveness of the BONEBRIDGE
	implant in adults with mixed or conductive hearing loss.
	Secondary: To assess post-operative audiometric and speech
	perception outcomes with BONEBRIDGE, compared to unaided pre-
	operative performance as well as report on intraoperative experience.
Endpoints:	1. Subjects will demonstrate significant improvement in AzBio
(Primary)	Sentence score in noise in the implanted ear at three (3) months post-
	activation, compared to unaided pre-operative performance.
	2. Safety data will be collected and reported as the number and
	proportion of subjects experiencing known risks of the BONEBRIDGE
(Cocondon)	implant through three (3) months post-activation.
(Secondary)	1. Subjects will demonstrate similar or better scores on CNC words in
	quiet in the implanted ear at three (3) months post-activation, compared to unaided pre-operative performance.
	2. Subjects will demonstrate similar or better soundfield thresholds in
	the implanted ear at three (3) months post-activation, compared to
	pre-operative unaided soundfield thresholds.
	3. Subjects will demonstrate similar or better performance on the
	QuickSIN in the implanted ear at three (3) months post-activation,
	compared to unaided pre-operative performance.
	4. Subjects will demonstrate stable bone conduction thresholds at the
	device activation interval compared to pre-operative bone conduction
	thresholds.
Study Population:	Approximately thirty (30) total subjects, 18 years of age and older, will
, .p.	be implanted across three study sites in the United States and Canada.
	Fifteen (15) subjects with mixed hearing loss and fifteen (15) subjects
	with conductive hearing loss will be recruited.
Description of Sites	Three (3) sites will participate in the clinical trial. Two (2) sites will be
Enrolling Participants:	located in the United States, and one (1) site will be in Canada.
Description of Study	Subjects will be implanted with the MED-EL BONEBRIDGE Bone
Device:	Conduction Implant (BCI 601 or BCI 602). Subjects will be fit with the
	SAMBA Audio Processor using SYMFIT software. The system is
	commercially available in the United States and Canada.
Study Duration:	Enrollment is expected to last eighteen (18) months, while subject
	follow-up will last an additional four (4) months. Therefore, the study
	duration is anticipated to be twenty-two (22) months, from opening
	of enrollment to completion.
Participant Duration:	Each subject's participation in the clinical trial will last approximately
	four (4) months.

## **SCHEMATIC OF STUDY DESIGN**

Enrollment/
Baseline

- •Informed Consent
- Medical Assessment
- Audiometric Assessment
- Speech Testing
- Subjective Questionnaires

Surgery

• Bone Conduction Implant Surgery

Activation (2 weeks post-surgery) Audiometric Assessment

Evaluation I (2 wks postactivation) • Soundfield Threshold Testing

Evaluation II (1 mo. postactivation)

- Soundfield Threshold Testing
- Speech Testing

Evaluation III (3 mos. postactivation)

- Soundfield Threshold Testing
- Speech Testing
- Subjective Questionnaires

## 1 PURPOSE

The purpose of this investigation is to assess safety and effectiveness of the BONEBRIDGE Bone Conduction Implant for adults with mixed or conductive hearing loss. Study candidates will demonstrate bone conduction thresholds better than 45 dB. Surgical and performance outcomes will be collected through three months post-activation.

## 2 INTRODUCTION

## 2.1 BACKGROUND INFORMATION

The MED-EL BONEBRIDGE Bone Conduction Implant is a transcutaneous, active bone conduction implant that was first implanted in 2011 in a European multicenter clinical trial. (Sprinzl, et al., 2013) Results from the initial clinical trial demonstrated effectiveness in restoring hearing and a low number of adverse events for subjects with mixed and conductive hearing loss. The BONEBRIDGE consists of an implantable part, the Bone Conduction Implant (BCI), and the external audio processor. The BCI consists of a magnet surrounded by the receiver coil, the electronics, a bendable transition, and the Bone Conduction-Floating Mass Transducer (BC-FMT).

A long history of experience with other available bone conduction implants, such as percutaneous BAHA devices, resulted in positive audiological outcomes but a high number of adverse events such as skin reactions, loss of osseointegration, and revision surgery. (Badran, Bunstone, Arya, Suryanarayanan, & Mackinnon, 2006) Development of the transcutaneous BONEBRIDGE system offers an intact skin solution that does not require osseo-integration and, thus, provides an active bone conduction implant with fewer post-operative complications.

In 2016, Schmerber et al. published on 13 adult patients with mixed or conductive hearing loss implanted with the BONEBRIDGE. (Schmerber, et al., 2016) No complications, device failures, or revision surgeries were reported in this patient group through 12 months post-implantation. Subjects demonstrated significant improvements in functional gain, speech perception in quiet, and speech perception in noise. These results were further confirmed by Weiss et al., who published data on 18 subjects implanted with BONEBRIDGE for mixed or conductive hearing loss. (Weiss, et al., 2016) No cases of infection or other complications were reported in this study. Riss et al. demonstrated similar results in subjects with mixed hearing loss and with atresia. (Riss, et al., 2014) On average, subjects with mixed hearing loss demonstrated 24.7 dB of functional gain, while subjects with atresia demonstrated 32.5 dB of functional gain. The authors hypothesized that the group with atresia demonstrated higher functional gain because they had a larger pre-operative air-bone gap.

A variety of surgical approaches can be used to properly place the BONEBRIDGE, and preoperative imaging is recommended in the planning of BONEBRIDGE placement. A review published in 2015 reported on five publications including 20 patients. (Zernotti & Bravo Sarasty, 2015) Surgical approaches encompassed transmastoid, retrosigmoid, and middle fossa or "above the temporal line." Patient anatomy and history of prior ear surgery can influence the decision on which surgical approach is most appropriate. Functional gain ranging from 24 to 43 dB was reported in these five publications.

As published by Sprinzl & Wolf-Magele in 2015, 29 studies reported improvements in audiological outcomes and low complication rates. (Sprinzl & Wolf-Magele, 2016) Twelve studies reporting safety outcomes showed a total of six minor complications across three studies, with nine studies reporting no adverse events through at least six months of follow-up. These studies included a wide range of demographic and surgical factors, indicating that BONEBRIDGE is safe for use in the approved population and with the recommended surgical techniques. Additionally, 11 studies demonstrated improved audiological outcomes in both short-term and long-term data, indicating that BONEBRIDGE is also effective in the approved population.

The current study proposes to collect multicenter safety and effectiveness data across North America. Audiological and surgical outcomes will be collected and reported, as well as the occurrence of any known risks with BONEBRIDGE implantation. The subject population will meet the current indication criteria and investigators will follow the recommended surgical techniques.

## 2.2 POTENTIAL RISKS AND BENEFITS

## 2.2.1 KNOWN POTENTIAL RISKS

The known potential risks of implantation in the currently approved population are as follows:

- Post-surgery displacement of the implant
- Post-surgical translocation of the BC-FMT
- Extrusion of the implant
- Skin-related issues
- Infection
- Tinnitus
- Vertigo
- Headache
- Dural erosion/compression
- CSF leak
- Meningitis
- Bleeding/hematoma or subdural hematoma
- Facial nerve injury
- Intra-operative complications, including from anesthesia

In rare cases, post-operative device failure or decrease in device performance may occur. Some serious complications may result in revision surgery.

It is recommended that bone conduction implant recipients receive age-appropriate vaccinations, including a pneumococcal meningitis vaccine prior to implantation.

## 2.2.2 KNOWN POTENTIAL BENEFITS

Subjects may experience an improvement in sound detection and speech perception abilities, as compared to preoperative abilities with or without acoustic amplification.

Subjects may also obtain subjective benefit after implantation, as compared to their experience with or without acoustic amplification.

#### 3 OBJECTIVES

All subjects will receive a MED-EL BONEBRIDGE Bone Conduction Implant.

The primary objective is to assess safety and effectivenss of the MED-EL BONEBRIDGE Bone Conduction Implant for adults with mixed or conductive hearing loss.

Secondary objectives will assess post-operative audiometric and speech perception outcomes with BONEBRIDGE, compared to unaided pre-operative performance as well as report on intraoperative experience.

## 4 STUDY DESIGN AND ENDPOINTS

## 4.1 DESCRIPTION OF THE STUDY DESIGN

Approximately 30 subjects will be enrolled across three centers in this single-arm, repeated measures study, where each subject serves as his or her own control. Of the 30 subjects recruited into the study, 15 subjects with mixed hearing loss and 15 subjects with conductive hearing loss will be recruited across all three sites. After enrollment/baseline assessment confirms candidacy, qualified individuals will receive a BONEBRIDGE Bone Conduction Implant. Each subject will subsequently be fit with a SAMBA Audio Processor.

Activation will occur at two weeks post-implantation. Follow-up evaluations will occur at two weeks, one month, and three months post-activation. Soundfield thresholds, as well as speech perception testing in quiet and in noise, will be measured at the follow-up intervals. Results will be compared to the pre-operative unaided condition. In addition to any complications reported on a surgical questionnaire, safety outcomes will be collected and reported as the number and proportion of subjects experiencing a known risk. The three-month interval will be considered the primary safety and effectiveness endpoint.

## 4.2 STUDY ENDPOINTS

## 4.2.1 PRIMARY ENDPOINTS

Primary endpoints are as follows:

- 1. Comparison of AzBio sentence score in noise with the BONEBRIDGE at three months post-activation to the pre-operative unaided score. Testing will be completed in the soundfield at 60 dB SPL with a +5 dB signal-to-noise ratio (SNR). Improvement will be defined as equal to or greater than 10 percentage points.
- 2. Number and proportion of subjects experiencing known risks, as listed above in Section 2.2.1.

## 4.2.2 SECONDARY ENDPOINTS

Secondary endpoints are as follows:

- CNC word score in quiet with the BONEBRIDGE at three months post-activation in the
  individual implant ear(s), compared to the pre-operative unaided score in the same ear.
  Testing will be completed in the soundfield at 60 dB SPL. Scores at three months will be
  similar to or better than scores at the pre-operative interval. Similar is defined as within
  10 percentage points, while better than is defined as equal to or greater than a 10percentage-point change. Subjects will be classified as improved, similar, or worse at
  three months post-activation.
- 2. Soundfield thresholds with the BONEBRIDGE at three months post-activation in the individual implant ear(s) at 500-4000 Hz, compared to pre-operative soundfield thresholds in the same ear. Thresholds at three months will be similar to or better than scores at the pre-operative interval. Similar is defined as thresholds within 15 dB at five or more of the frequencies tested, while better is defined as a 15 dB improvement in thresholds at three or more frequencies tested. Subjects will be classified as improved, similar, or worse at three months post-activation.
- 3. QuickSIN score with the BONEBRIDGE at three months post-activation in the individual implant ear(s), compared to the pre-operative unaided score in the same ear. Scores at three months will be similar to or better than scores at the pre-operative interval. Similar is defined as within 1 dB SNR, while better than is defined as equal to or greater than than a 1 dB SNR decrease. Subjects will be classified as improved, similar, or worse at three months post-activation.
- 4. Bone conduction thresholds from the device activation interval will be compared to the pre-operative interval to assess stability in the implant ear(s). A worsening in bone conduction thresholds is defined as a 15 dB or greater decrease. Bone conduction thresholds will be considered stable if no more than two frequencies demonstrate a worsening.

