## 7 STUDY PROCEDURES AND SCHEDULE

## 7.1 STUDY PROCEDURES

## 7.1.1 STUDY SPECIFIC PROCEDURES

The following procedures will be performed over the duration of the study and will be documented for each subject enrolled in the study.

- Informed Consent (IC): Investigators will review the IC with potential subjects and obtain signature prior to initiating study activities.
- Medical Assessment: Subjects should be evaluated for their ability to undergo surgery. This
  should include a chart review to document prior surgeries and known health conditions, as
  well as ear-related history. All subjects should also undergo a complete otologic exam and
  radiologic assessment, for proof of adequate anatomy to enable placement of the implant.
- Surgery: BONEBRIDGE surgery will be performed once a subject has consented to participating in the study and completed pre-operative assessment.
- Unaided Thresholds: Unaided air conduction thresholds will be measured pre- and postoperatively at 250, 500, 1000, 2000, 3000, 4000, 6000, and 8000 Hz. Bone conduction thresholds will also be measured at 500, 1000, 2000, 3000, and 4000 Hz in order to determine whether hearing loss is conductive or mixed.

- Sentence Testing: AzBio sentences in noise will be administered at 60 dB SPL with a signalto-noise ratio of +5 dB SNR as the primary outcome measure. Sentence testing will occur in the unaided condition pre-operatively and with the BONEBRIDGE post-operatively. One list will be presented per condition.
- Monosyllabic Word Testing: CNC words in quiet will be administered at 60 dB SPL as a secondary outcome measure. Word testing will occur in the unaided condition preoperatively, and with the BONEBRIDGE post-operatively. One list will be presented per condition.
- Soundfield Thresholds: soundfield thresholds will be measured in the implant ear only at 500, 1000, 2000, 3000, and 4000 Hz pre-operatively and post-operatively.
- Signal-to-Noise Ratio Testing: The QuickSIN will be administered at 60 dB SPL preoperatively in the unaided condition and post-operatively with the BONEBRIDGE. This will be reported as a Signal-to-Noise Ratio Loss.
- Subjective Questionnaires: Subjects will complete the SSQ12 questionnaire (Noble, Jensen, Naylor, Bhullar, & Akeroyd, 2013) and HDSS questionnaire (Luetje, et al., 2002) preoperatively and post-operatively.
- BONEBRIDGE Programming: Programming of the audio processor should occur at each interval after device activation.

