## 10.2.3 ANALYSIS OF THE SECONDARY ENDPOINT(S)

Secondary endpoints will not be formally tested but will be summarized using appropriate descriptive statistics.

The number and percentage of subjects performing similarly or better on CNC words, soundfield thresholds, QuickSIN, and bone conduction thresholds at 3 months post-activation, compared to the pre-operative unaided condition, will be presented. The formal definitions of what is considered worse, similar, and better are presented in section 4.2.2.

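### The soundfield 'similar' rule requires all five tested frequencies to be within 15 dB, so an ear that improves markedly at only one or two meets neither 'similar' nor 'better' and, by elimination, becomes 'worse'

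*Combined protocol and SAP*

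**What the plan says.** Section 4.2.2, item 2, sets two rules for the three-month soundfield comparison with the pre-operative thresholds:

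- 'Similar': "Similar is defined as thresholds within 15 dB at five or more of the frequencies tested".
- 'Better': "better is defined as a 15 dB improvement in thresholds at three or more frequencies tested".

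It then fixes the permitted outcomes: "Subjects will be classified as improved, similar, or worse at three months post-activation". It states no rule for 'worse'.

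Section 7.1.1 fixes the number of frequencies: "soundfield thresholds will be measured in the implant ear only at 500, 1000, 2000, 3000, and 4000 Hz". The baseline, two-week and three-month visits in section 7.2 give the same 500 to 4000 Hz range.

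Section 10.2.3 reports the result as "The number and percentage of subjects performing similarly or better on CNC words, soundfield thresholds" and the other secondary measures. For the rules it refers back: "The formal definitions of what is considered worse, similar, and better are presented in section 4.2.2". The same section limits what rests on the result: "Secondary endpoints will not be formally tested".

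**The concern.** With five frequencies tested, the words 'or more' in the 'similar' rule do nothing, and every frequency has to be within 15 dB. A gain of more than 15 dB at one frequency is then enough to disqualify an ear from 'similar', but 'better' is not reached until three frequencies have improved. Ears with one or two large gains fall between the two rules.

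The ordering this produces is wrong. An ear with no change counts as a success, while the same ear with a large gain at one or two frequencies does not. Because section 10.2.3 points to a definition of 'worse' that item 2 does not contain, whoever analyses the data must either label these improved ears 'worse' or invent a rule after seeing the results. At stake is the accuracy of the one summary figure planned for this endpoint.

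**Working it through.** **Inputs.** Five frequencies (section 7.1.1). 'Similar' means within 15 dB at five or more, and 'better' means a 15 dB improvement at three or more (section 4.2.2, item 2). The documents give no count or percentage for this endpoint to reproduce.

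**Step 1: ears with no worsened frequency.** Let k be the number of frequencies improved by more than 15 dB, with the other 5 − k unchanged. 'Similar' requires 5 − k ≥ 5, so k = 0. 'Better' requires k ≥ 3.

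| k | Within 15 dB | Class under the written rules |
|---|---|---|
| 0 | 5 | similar |
| 1 | 4 | neither |
| 2 | 3 | neither |
| 3, 4, 5 | 2, 1, 0 | better |

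For n tested frequencies, k = 2 would be 'similar' only if n − 2 ≥ 5, so these two cut-offs leave no such gap only when n is 7 or more. Here n is 5.

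**Step 2: all patterns.** Score each frequency as improved by more than 15 dB, within 15 dB, or poorer by more than 15 dB. That gives 3^5 = 243 patterns:

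- 51 better, of which 35 also contain a worsened frequency;
- 1 similar;
- 5 + 10 = 15 with improvement at one or two frequencies and no worsening, in neither class;
- 176 not better and containing a worsened frequency.

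The total is 51 + 1 + 15 + 176 = 243. This checks completeness; the counts are not probabilities.

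**Step 3: a change of exactly 15 dB.** If it counts as within 15 dB, three frequencies improved by exactly 15 dB with two unchanged satisfy both rules. If it does not count, one or two gains of exactly 15 dB also fall into the gap. Item 2 does not say which reading applies.

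**Step 4: how many subjects.** No standard deviation for soundfield gain is given, so only an assumption-based range is possible. The means come from the study cited in section 2.1: "subjects with mixed hearing loss demonstrated 24.7 dB of functional gain, while subjects with atresia demonstrated 32.5 dB of functional gain". Atresia stands in for conductive loss. Simulated gain = mean + normal ear effect + normal frequency effect, rounded to 5 dB steps, with one mean at every frequency, one ear per subject and 1,000,000 ears per setting. The between-ear and within-ear SDs were each set to 4, 6, 8, 10 or 12 dB. Improvement-only ears in neither class, for a 15 + 15 cohort:

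| Between / within SD (dB) | Exactly 15 dB outside 'within' | Exactly 15 dB inside 'within' |
|---|---|---|
| 4 / 4 | 0.17% (0.05 of 30) | 0.09% (0.03 of 30) |
| 8 / 4 | 2.69% (0.81) | 0.77% (0.23) |
| 8 / 8 | 4.47% (1.34) | 3.19% (0.96) |
| 10 / 10 | 7.14% (2.14) | 5.71% (1.71) |
| 12 / 12 | 8.83% (2.65) | 7.92% (2.38) |

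Over the whole grid, 87% to 99.8% of ears meet 'better' outright.

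**Step 5: uneven gain.** With an assumed profile of 45, 40, 20, 10 and 8 dB (mean 123/5 = 24.6 dB), about 8% of ears are affected at SDs 4/4 and about 16% to 18% at 8/8. The Step 4 range is therefore not a bound.

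**The case against.** The strongest reply is that 'within 15 dB' means no more than 15 dB poorer. Item 2 states its aim as scores similar to or better than baseline, and item 4 defines change only as worsening. On that one-sided reading the partly improved ears are 'similar' and the gap closes. But the text does not say so. Items 1 and 3 use the same 'within' form beside a separate 'better' class, which reads naturally as two-sided. A one-sided reading would also make every improvement-only 'better' ear 'similar' as well, so a precedence rule would still be needed.

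A second reply is that 'worse' is inferred: nothing in the protocol labels these ears so, and an analyst could leave them unclassified. That is fair as to the label. Their exclusion from the similar-or-better count follows directly from the two written rules.

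A third is that the size is weakly grounded. That stands. No SD is available, the means come from a cited study, and unevenness across frequencies, which creates the gap, can push the figure above the simulated range.

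Finally, the remedy has to supply a definition of 'worse' that the protocol lacks, and one worsened frequency is stricter than item 4, which tolerates two. Lowering the 'similar' cut-off to three of five would also close the gap for improvement-only ears. However, it makes 51 patterns 'similar', of which only 1 + 5 + 10 = 16 have no worsened frequency. The other 51 − 16 = 35 contain one and are excluded under the present rule. The proposal below leaves that exclusion in place.

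**Conclusion.** The concern holds, as a minor one. Confidence is high that the two rules leave a gap and that partly improved ears fall outside the reported percentage. The label 'worse' follows only by elimination among the three permitted classes.

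Confidence in the size is low. The illustrative range of 0.09% to 8.8%, roughly none to two or three of 30 subjects, rests on assumed SDs, a single mean at all frequencies, atresia standing in for conductive loss, and one ear per subject although bilateral implantation is allowed. An uneven gain profile can give more.

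The effect on conclusions is limited. The endpoint is secondary and descriptive, no success threshold is attached to the percentage, and the error understates benefit. The primary AzBio test, its power and the safety endpoint are unaffected.

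**What to change.** Before the three-month soundfield data are analysed, amend section 4.2.2, item 2, so that each ear falls in exactly one class:

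- **Better:** improvement of at least 15 dB at three or more of the five frequencies (unchanged).
- **Similar:** not better, and no frequency poorer by more than the 15 dB tolerance.
- **Worse:** not better, and at least one frequency poorer by more than that tolerance.

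State once whether exactly 15 dB poorer is inside the tolerance; item 4 counts 15 dB or more as worsening for bone conduction. Report separately any 'better' ear that also has a worsened frequency, since the existing 'better' rule permits it.

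The change can only raise the percentage, and under section 9 the sponsor reviews case report forms as they arrive. The percentage under the current protocol wording should therefore be reported alongside the corrected one.

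The proposed rules were checked on 7^5 = 16,807 profiles, with a change of −20, −15, −10, 0, 10, 15 or 20 dB at each frequency. Every profile receives exactly one class and none loses similar-or-better status. Those that gain it (1,890 with exactly 15 dB outside the tolerance, 3,200 with it inside) have no frequency poorer beyond the tolerance.

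The cost is a wording change, IRB approval of the amendment under section 11.2, and one extra reported percentage. Thresholds are already recorded at all five frequencies, so no new data are needed.
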